The primary analysis will be conducted into 2 steps starting with testing for NI of GMTs between RIV4 and IIV4. If NI of GMTs based on the 4 strains is demonstrated, then NI for SC will be also tested.

Step 1: Geometric Mean Titers

Assuming that log10 transformation of the data follows a normal distribution, the log10 (data) will be used for the statistical analysis, then antilog transformations will be applied to the results of calculations, in order to provide the results in terms of geometric means (GMs).

The statistical methodology is based on a 2-sided 95% CI of the ratio of the GMTs (RIV4 divided by IIV4) at 28 days after the last vaccination. Non inferiority for GMTs is demonstrated if the lower limit of the 2-sided 95% CI of the GMT ratio is > 0.667 for each of the 4 virus strains.

ANCOVA will be conducted for each strain with a model including the terms log10 of HAI titer at D01, priming status, age subgroup, season and the treatment represented by the vaccine administered as independent factors, and log10 HAI titer of each virus strain separately of the last vaccination as a response variable. ANCOVA will be conducted using Proc Mixed in SAS (all terms in the model are fixed). In Proc Mixed, the "Estimate" statement will allow to derive the difference (RIV4 minus IIV4) of the Least Squares-means and the 95% CI in their original log10 values. By exponentiating the difference (RIV4 minus IIV4) and its 95% CI; the 95% CI of ratio (RIV4/IIV4) will be obtained and be used to derive GMTs NI final results.

Step 2: Seroconversion

The statistical methodology will be based on a 2-sided 95% CI of the difference in SC rates (RIV – IIV4) 28 days after the final vaccination. Non-inferiority for SC will be demonstrated if the lower limit of the 2-sided 95% CI is > -10% for the 4 strains. The 95% CI of the rate difference will be computed using the Wilson Score method without continuity correction

Non-inferiority will be assessed on PPAS as the main analysis set and will be confirmed on the FAS.

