3.4.2 Primary Endpoints

The immunogenicity parameters will be calculated in each study group with their 95% CIs using the exact binomial distribution (Clopper-Pearson method) for proportions and using normal approximation of log-transformed for GMTs.

Statistical Methodology for analyzing the primary 8 endpoints (GMTs and SC rates).

Non-inferiority of RIV4 as compared to IIV4 in participants 3 to 8 years of age will be conducted for GMTs and SC rates.

For each strain, the NI methodology will be applied to compare the post-vaccination GMTs and the SC rates between the groups using a 1-sided Type I error rate of 0.025 with the given individual hypothesis.

The primary analysis will be conducted into 2 steps starting with testing for NI of GMTs between RIV4 and IIV4. If NI of GMTs based on the 4 strains is demonstrated, then NI for SC will be also tested.

Step1: Geometric Mean Titers

Assuming that log10 transformation of the data follows a normal distribution, the log10 (data) will be used for the statistical analysis, then antilog transformations will be applied to the results of calculations, in order to provide the results in terms of geometric means (GMs).

The statistical methodology is based on a 2-sided 95% CI of the ratio of the GMTs (RIV4 divided by IIV4) at 28 days after the last vaccination. Non inferiority for GMTs is demonstrated if the lower limit of the 2-sided 95% CI of the GMT ratio is > 0.667 for each of the 4 virus strains.

As appropriate according to the number of participants in the respective subgroups, ANCOVA will be conducted for each strain with a model including the terms log10 of HAI titer at D01, priming status, age subgroup, season and the treatment represented by the vaccine administered as independent factors, and log10 HAI titer of each virus strain separately of the last vaccination as a response variable. ANCOVA will be conducted using Proc Mixed in SAS (all terms in the model are fixed). In Proc Mixed, the "Estimate" statement will allow to derive the difference (RIV4 minus IIV4) of the Least Squares-means and the 95% CI in their original log10 values. By exponentiating the difference (RIV4 minus IIV4) and its 95% CI; the 95% CI of ratio (RIV4/IIV4) will be obtained and be used to derive GMTs NI final results.

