In the interim analysis, the statistical methodology will be based on a 2-sided 95% CI of the ratio of the GMTs (RIV4 divided by IIV4) at 28 after the last vaccination. NI for GMTs will be demonstrated if the lower limit of the 2-sided 95% CI of the GMT ratio is > 0.667 for each of the 4 virus strains. The 95% CI will be calculated using normal approximation of log-transformed titers. The Per-Protocol Analysis Set (PPAS) will be used as the primary analysis set.

Confidential/Proprietary Information Page 19 of 40

Step 2: Seroconversion rates

The statistical methodology is based on a 2-sided 95% CI of the difference in SC rates (RIV4 minus IIV4) at 28 days after last vaccination. NI for SC rates is demonstrated if the lower limit of the 2-sided 95% CI is > -10% for the 4 strains. The 95% CI of the rate difference is computed using the Wilson Score method without continuity correction.

As a sensitivity analysis, a generalized linear model (binomial-identity model) based on a link function named "identity link" will be used. The regression coefficient for the treatment (vaccines administered) in the binomial-identity model represent the proportions difference (difference between RIV4 and IIV4). The model will include priming status, age subgroup, season, and the treatment term (represented by the vaccines administered) as independent factors. The difference (RIV4 – IIV4) and its 95% CI obtained will be used to derive the SC NI results.

In the sensitivity analysis, the statistical methodology will be based on a 2-sided 95% CI of the difference in SC rates (RIV4 – IIV4) at 28 days after last vaccination. The NI for SC rates will be demonstrated if the lower limit of the 2-sided 95% CI is > -10% for the 4 strains.

In the interim analysis, no sensitivity analysis will be conducted for SC due to the limited number of participants included in the interim analysis.

Non-inferiority will be assessed on PPAS as the main analysis set and will be confirmed on the FAS.

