3.5.2 Immunogenicity

Sanofi decided to assess the likelihood of success in this study at the end of study. Hence, it was decided to calculate the predictive power of each endpoint (GMT and SC) based on data collected at the end of the first season, which is the flu season 2022-2023.

The predictive power is defined as the probability that the final study result will be successful, given the data observed thus far – at the time of the interim analysis (4).

Confidential/Proprietary Information Page 24 of 40 In addition, the following summary statistics will be generated and presented:

- GMT for each strain at D01 and D29 or D57
- The geometric mean titer ratios (GMTR): geometric mean of the post-vaccination/pre-vaccination ratio for each strain
- Seroconversion rate at D29 or D57 based on the baseline titer at D01
- Proportion of participants with titers ≥ 1:40 (1/dilution [dil]) for each strain at D01 and D29 or D57.

The immunogenicity analysis will be conducted on the PPAS, and on FAS if the attrition rate from FAS to PPAS is greater than 10%.

3.5.2.1 Calculating the individual PPoS (GMTs and SC rates).

In-house, 2 SAS Macros are to be used in calculating PPoS based on simulations. The first SAS macro will calculate PPoS of GMT for each vaccine strain separately, and the second SAS macro will calculate PPoS of seroconversion rate for each vaccine strain separately.

All NI inferiority testing will be conducted as per Section 3.1.

The main steps to calculate the individual PPoS for GMT and SC rate are described in Table 3.3 and

Table 3.4 respectively.

Table 3.2 presents the current numbers of participants at main study timepoints considered in the analysis.

 Table 3.2: Study Design – Current Planned Number of Randomized Participants at Main

 Study Timepoints

		RIV4	IIV4
Study Planning	Number of participants to	$N_{\rm F} = 706$	$N_{\rm C} = 706$
(protocol & SAP)	be enrolled by the end of		
	the study		
Interim	Approximate number of	$N_{i1F} = 183$	$N_{i1C} = 183$
	participants enrolled up to		
	interim analysis		
Remainder of the	Approximate number of	$N_{rF} = N_F - N_{i1F}$	$N_{rC} = N_C - N_{i1C}$
Study	participants to be enrolled	(706-183=523)	(706-183=523)
	by the end of the study		

Main Steps	Steps' Definition of each of the 4 Antigens GMT separately
1	The total number of participants to be enrolled in the whole study is approximately 1412, randomized with a 1:1 ratio between RIV4 and IIV4 vaccine groups.

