	The interim data includes 366 randomized participants, randomized with a 1:1 ratio between the vaccine groups. The PPAS will be used as the main analysis set for PPoS calculation.
	All the randomized participants in the remainder of the study are going to be generated with a 1:1 ratio between the vaccine groups.
2	 At the interim analysis: For each vaccine group and each strain calculate the mean and standard deviation of LOG10(titer) use the predictive distribution to derive B times datasets (e.g. 100.000) of the participants not yet enrolled in the study (to reach the approximately 1200 planned PPAS subjects overall in both vaccines) – with a seed value in SAS of 1545313 (for RIV4) and 4878646 (for IIV4)
3	Combine the interim dataset and the B datasets of the after interim to constitute the final and complete B datasets using the same sequence number. The final complete B datasets will be used to derive the 2-sided 95% CI of the difference (between RIV4 and IIV4) between the LOG10(mean) of each antigen for each one of the B complete datasets.
4	Use the 2-sided 95% CI of the difference (between the mean LOG10(titer) of RIV4 and the mean of LOG10(titer) of IIV4) for each B dataset to calculate the PPoS by deriving the proportion of datasets with the NI success.
	NI success in each complete dataset of each vaccine strain will be determined by comparing the lower bound of the 95% CI to the NI margin (-0.176)

Table 3.3: Description and Definition of the Main Steps in Calculating PPoS for NI Based onGMTs for each Vaccine Strain, Separately

Main Steps	Steps' Definition of each of the 4 vaccine Strains separately
1	The total number of participants to be enrolled in the whole study is approximately 1412, randomized with a 1:1 ratio between RIV4 and IIV4 vaccine groups.
	The interim data includes 366 randomized participants, randomized with a 1:1 ratio between the vaccine groups. The PPAS will be used as the main analysis set for PPoS calculation.
	All randomized participants in the remainder of the study are going to be generated with a 1:1 ratio between the vaccine groups.
2	At the interim analysis:

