Correlations between vaccines' strain titers are generally low. Hence, the overall PPoS for NI of the 4 GMTs will be calculated by multiplying the 4 individual PPoS for NI calculated based on the GMTs. Likewise, the overall PPoS for NI of the 4 SCs will be calculated by multiplying the 4 individual PPoS for NI calculated based on SCs.

The study overall PPoS will be calculated by multiplying the 8 individual PPoS (GMTs and SC rate) calculated above.

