4.2.3.3 Seroconversion

For HAI assay, seroconversion is defined as a binary indicator. If a pre-vaccination (D01) titer < 10 (1/dil): post-vaccination titer ≥ 40 (1/dil) on 28 days after the last vaccination (D29 or D57), or ≥ 4 -fold-rise for participants with a pre-vaccination titer ≥ 10 (1/dil), the derived seroconversion indicator will be "Yes", otherwise will be "No".

Note: if pre-vaccination (D01) or post-vaccination (D29 or D57) value is missing, the seroconversion is missing.

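### The eight-test futility PPoS multiplies GMT and SC of the same strain as if they were independent, which understates the chance of success; separately, the simulated GMT test is not the planned ANCOVA

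*SAP*

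**What the plan says.** SAP 3.5.2 sets the target: "The predictive power is defined as the probability that the final study result will be successful", given the interim data. Protocol 9.1 requires all eight non-inferiority hypotheses (four GMT, four SC) to be rejected, so the target is a joint probability.

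SAP 3.5.2.1 computes each strain's GMT PPoS with one macro (Table 3.3) and each strain's SC PPoS with another (Table 3.4). SAP 3.5.2.2 combines them: "The study overall PPoS will be calculated by multiplying the 8 individual PPoS (GMTs and SC rate) calculated above". Its justification is "Correlations between vaccines' strain titers are generally low". It does not discuss GMT against SC of the same strain.

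SAP 4.2.3.3 says "For HAI assay, seroconversion is defined as a binary indicator", derived from the D01 titer and the D29 or D57 titer. The latter is also the GMT response.

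For the final GMT test, Protocol 9.4.2 says "ANCOVA will be conducted for each strain with a model including the terms log10 of HAI titer at D01, priming status, age subgroup, season" and treatment. SAP 3.4.2 repeats this with a qualification: "As appropriate according to the number of participants in the respective subgroups, ANCOVA will be conducted for each strain with a model including the terms". For the interim, SAP 3.4.2 says "The 95% CI will be calculated using normal approximation of log-transformed titers", and Table 3.3 applies an unadjusted difference in mean log10 titer to each completed dataset.

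SAP 3.5 and 3.5.2.3 attach the (redacted) futility guidance to the eight-test PPoS. Protocol 9.5 attaches its (redacted) value to the PPoS of the four GMT tests.

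**The concern.** If two events are positively dependent, the probability that both occur exceeds the product of their separate probabilities. A vaccine group with high post-vaccination titers tends to have both a high GMT and a high SC rate, so the two tests for a strain are positively dependent. The SAP's argument concerns strain against strain and leaves this pairing uncovered. Because the two macros run separately, nothing later recovers the joint figure. The error has one direction, toward stopping, and it enters the figure to which the SAP attaches its guidance.

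Two related points affect the same figure. PPoS is defined on the final result, but the simulated GMT test leaves out the baseline titer and the other ANCOVA terms. And the two documents name different statistics for the threshold, so one interim could trigger the guidance under one document and not under the other.

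**Working it through.** **1. The plan's own power figures (SAP 3.2).** 600 evaluable per arm, SD 0.6 on log10, margin log10(1.5) = 0.176, one-sided 0.025.
- GMT: SE = 0.6 × √(2/600) = 0.0346; power = Φ(0.176/0.0346 − 1.96) = 99.91% per strain; 0.9991⁴ = 99.6%, as stated.
- SC: Φ(0.10/√(2p(1−p)/600) − 1.96) = 93.4% at p = 0.5 and 96.6% at p = 0.7 (stated 93.7% and 96.7%). The product over four strains is 81.3% (stated 82.0%), and overall 81.0% (stated 82.0%).
- At this stage the product does little harm: the joint power is 81.1–81.3%, because the GMT power is near 1.

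**2. Predictive model for one strain.** Interim evaluable per arm is assumed to be 366 × 0.85 / 2 ≈ 155, leaving 445 to come. With a flat prior, the final difference given interim difference d is normal with mean d and SD τ = (445/600) × s × √(2/155 + 2/445).
- GMT: s = 0.6, τ = 0.0587. SC at 0.5: s = 0.5, τ = 0.0489.
- PPoS = Φ(z), with z = (d + margin − 1.96 s √(2/600)) / τ.
- The joint PPoS for a strain is the bivariate normal probability at (z for GMT, z for SC) with correlation r.

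The documents do not give r. Simulated HAI-type titers (54 scenarios: 2-fold dilutions, values below 10 set to 5, SC fixed at 0.5 or 0.7) give r from 0.47 to 0.79, median 0.66. The range 0.5 to 0.7 is used below.

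Worked case, ratio 0.80 and SC difference −5 points:
- GMT: z = (−0.0969 + 0.1761 − 0.0679)/0.0587 = 0.19, PPoS 57.6%.
- SC: z = (−0.05 + 0.10 − 0.0566)/0.0489 = −0.13, PPoS 44.6%.
- Product 26%; joint 34–37%.

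| Interim GMT ratio / SC difference | Product | Joint, r = 0.5 to 0.7 |
|---|---|---|
| 1.0 / 0 | 79% | 80–81% |
| 0.80 / −5 points | 26% | 34–37% |
| 0.70 / −8 points | 4.8% | 10–13% |

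**3. All eight tests.** Equal vaccines, SC 0.5/0.5/0.7/0.7, strains independent as the SAP assumes, 200,000 simulated interims.

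| | Product | Joint |
|---|---|---|
| Median PPoS, r = 0.5 | 14.0% | 17.0% |
| Median PPoS, r = 0.7 | 14.6% | 19.5% |
| Interims at or below 1% | 10–11% | 5–6% |
| at or below 5% | 28% | 19–22% |
| at or below 10% | 41% | 32–35% |
| at or below 20% | 59–60% | 51–55% |

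The cut-offs are assumed and cover r = 0.5 to 0.7. A patient-level check (600 interims, future children resampled whole by Bayesian bootstrap, Wilson-score CI, r about 0.65) gave medians of 17% and 21%. At the 10% cut-off it gave 40% and 31%, and the joint figure exceeded the product in 98% of interims.

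If the draws are plug-in, the 2s²/155 term drops out of τ². The medians become 17.0% vs 18.6% (r = 0.5) and 18.7% vs 21.5% (r = 0.7). At the 10% cut-off the shares are 42.6% vs 40.9% and 41.4% vs 38.7%.

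**4. Unadjusted test against ANCOVA, one strain.** Assumed baseline–post correlation 0.5, so the residual SD is 0.6 × √(1 − 0.25) = 0.52. A 1-SE baseline imbalance shifts the adjusted difference by 0.5 × 0.6 × √(2/155) = 0.034.
- Balanced baselines, unadjusted vs ANCOVA: 74% vs 82% at ratio 0.85; 12.4% vs 12.5% at 0.667; 2.6% vs 2.0% at 0.60.
- At 0.85, the ANCOVA figure is 60% if RIV4 baselines are 1 SE higher and 94% if 1 SE lower.
- With equal vaccines the means are 89% and 93%, but ANCOVA gives the lower figure in 22% of interims.

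This mismatch therefore has no fixed direction. It touches only the four GMT tests, because the final SC test is itself unadjusted.

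**5. Which statistic carries the threshold.** In the model of step 3, the median four-GMT PPoS is 66%, against 14–15% for the eight-test product. At or below 10%, the shares are 3% and 41%.

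**The case against.** The arithmetic is not in dispute; the case against concerns consequence.

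- **The cut-off is redacted and may have been set on the product scale.** In the same model the rank correlation between product and joint PPoS is 0.994 to 0.997. If the joint cut-off is moved to match the stopping frequency (10% on the product corresponds to about 12.6–14.4% jointly), the two agree in 96.5–97.4% of interims. This stands as far as it goes: the order of interims hardly changes. But the SAP defines the figure as a probability of success, a committee will read it as one, and nothing in the visible text says that the guidance was calibrated to a deliberately low product.
- **The gap is small at the extremes.** With the truth at both margins, practically every interim falls at or below 10% either way. With RIV4 better (ratio 1.2, SC +5 points, r = 0.7) the shares are 2.8% and 1.9%. True; the gap matters in intermediate cases, including equal vaccines. Even there, most of the low-PPoS risk comes from the small interim and remains after correction.
- **The size rests on undocumented choices.** The correlation is assumed, and plug-in draws shrink the gap. This stands. The SAP does not say which kind of draw it means, and it should.
- **The unadjusted interim CI is disclosed.** Yes, and SAP 3.5.2.1 also allows a complementary calculation within age-by-priming subsets. Disclosure makes it a stated simplification. It is still not the final test on which PPoS is defined, and the subset calculation does not bring in baseline titer.
- **The committee weighs the totality.** It also sees the component PPoS, subgroup results and safety, and Protocol 9.5 joins its criteria with and/or. This limits the harm but does not correct the number.
- **A joint model of eight censored titers is demanding.** Resampling whole children avoids having to specify one.

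**Conclusion.** The concern holds and should be fixed. As written, the study overall PPoS is not the probability that SAP 3.5.2 defines, and for any positive within-strain correlation it is too low. Under equal vaccines, flat-prior draws and r = 0.5 to 0.7, the median is understated by about 3 to 5 points. The share of interims at or below an assumed 10% cut-off is overstated by about 6 to 9 points. In weak single-strain interims the joint figure can be more than twice the product. With plug-in draws the differences are 1 to 3 points.

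The ANCOVA mismatch is real but has no fixed direction. The conflict over which statistic carries the threshold needs resolving whatever r is.

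The limits are firm. The guidance is non-binding, the cut-off is hidden, a changed recommendation cannot be shown, and the final tests and their type I error are unaffected.

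**What to change.** - Replace the multiplication in SAP 3.5.2.2 with one joint simulation. For each future child, draw the D01 and post-vaccination titers of all four strains together, for instance by resampling whole children within arm, and derive SC from those titers. Run the planned final tests (ANCOVA for GMT, Wilson-score CI for SC) on each completed dataset.
- Report the overall PPoS as the proportion of datasets passing all eight tests. Take the four-GMT, four-SC and individual PPoS from the same runs.
- State whether the draws are predictive (and with which prior) or plug-in. State how the season term is handled when the interim covers one season, for example by simulating future children with no season-by-vaccine interaction.
- Reconcile Protocol 9.5 and SAP 3.5 on which PPoS the threshold applies to.
- At the least, stop multiplying GMT and SC PPoS of the same strain.

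The cost is re-programming two in-house macros, more computing time for the ANCOVAs, revised SAP text and one reconciled sentence. No new data are needed, because both titers are already collected.

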3.5.2.3 FIC Futility Recommendation

FIC will review the results of the interim analysis and will make recommendations towards stopping for futility or safety reasons, based on the totality of information provided, including:

- The overall PPoS of the 4 GMTs and 4 SC NI statistical tests, based on a guidance of PPoS of less or equal **and**, considering also the trend across the different PPoS calculated:
 - The individual PPoS to meet NI for each vaccine strain and each parameter (Geometric Mean Titre [GMT] and Seroconversion [SC] rate)
 - The overall PPoS of the 4 GMTs NI statistical tests
 - The overall PPoS of the 4 SC NI statistical tests
- RIV4 immunogenicity results with regards to comparator in each age, priming status and baseline serological status subgroup will also be considered to inform the decision.
- Safety results will also be reviewed.

3.5.2.4 Data Included in the Interim Analysis

Immunogenicity and safety data will be summarized by vaccine group at the timepoint D29 after the last vaccination.

However, the listings of SAEs, grade 3 ARs and AEs leading to discontinuation will include all data (including the data collected beyond D29 after the last vaccination) included in the database.

Confidential/Proprietary Information Page 29 of 40

3.6 Data Monitoring Committee (DMC)

No independent Data Monitoring Committee (DMC) is planned.

Participant safety data will be continuously monitored by the Sponsor's internal safety management team (SMT), led by the Global Safety Officer, to detect any safety signals during the study period.

In addition, this study included an early safety data review (ESDR), when at least 10% of participants had been vaccinated and provided safety data for 7 days after vaccination.

A separate SAP was dedicated to theses analyses.

4 Complementary Information on Assessment Method

